9.3 Sample Size

We aim to enroll all practicing psychiatrists at the VA New York Harbor Healthcare System, but have conservatively estimated that 20 will enroll. This sample will allow us to study provider behavior during approximately 4,000 unique patient visits over 6 months. We calculated the level of power this will provide us to find a significant group effect on the proportion of patients prescribed a cessation medication by their psychiatrist (primary outcome 2). Our power calculation varied the intraclass correlation (ICC) of 0.05-0.15 based on a cluster-randomized trial of preventive care in primary care practices.⁵⁴ We estimate that 10% of patients in Arm 1 will receive a prescription.¹⁵ With the smallest ICC of 0.05, a type I error of 5%, and 80% power, 4,000 visits will provide us with enough power to detect a 21% or greater prescription rate in Arm 2. With the largest ICC of 0.15, a type I error of 5%, and 80% power, 4,000 visits will provide us with enough power to detect a 29% or greater prescription rate in Arm 2.

10 Ethics/Protection of Human Subjects

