4.1 Description of Study Design

This study will use a scientifically robust, mixed-methods, two-arm cluster-randomized study design. Study subjects are not NYULH employees or patients. We will implement a tobacco use clinical reminder for outpatient psychiatrists practicing at the VA New York Harbor Healthcare System (N = 20). Half of the psychiatrists will receive a reminder that encourages the psychiatrist to offer cessation medications and referral to cessation counseling to patients interested in quitting (Opt-In Reminder). The other half will receive a clinical reminder that includes a standing NRT order and a referral to cessation counseling that will automatically generate unless the provider actively opts-out (Opt-Out Reminder). Prior to implementation of the reminders, psychiatrists in both arms will receive a one-hour training on tobacco treatment and individual education outreach to demonstrate the clinical reminder and answer questions (academic detailing).

[figure not shown]
We will use VA administrative data extracted on all patient visits with a participating psychiatrist 6 months before and after implementation to calculate the study's primary outcomes: 1) the percent of patients screened for smoking, 2) the percent of smokers prescribed a cessation medication and 2) the percent of smokers referred to counseling. To assess intervention fidelity, we will use training logs to track psychiatrist attendance at group and academic detailing trainings. Over the intervention period, we will also conduct post-visit surveys with a cluster sample of 400 patients (20 per psychiatrist) to assess psychiatrist fidelity to the 3 A's approach. At the end of the intervention period, we will conduct semi-structured interviews with 12-14 psychiatrists (6-7/arm) asking about their perceptions of the intervention components. We will also analyze implementation observations (e.g., training observations, reflection memos) and documents (e.g., meeting minutes) for implementation barriers and facilitators. At six months, we will survey the clustered 400-patient sample again to evaluate the study's secondary outcomes: 1) patient use of cessation treatment in the prior 6 months and 2) self-reported 7-day abstinence at 6 months.

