One month before implementation of the provider training and reminders, all psychiatrists in the facility will be notified of the study at a required staff meeting. Psychiatrists will have the option at the meeting to ask questions and have the opportunity to opt-out of study participation. Psychiatrists will also have the opportunity to ask questions one-on-one with [name] before deciding whether to participate. Psychiatrist turn-over is low at the facility; however, during recruitment we will ask psychiatrists if they plan to leave in the next 6 months and only enroll those who have no plans to leave. When [name] used this approach to provider participation in a study implementing a new tobacco treatment model in VA NYHHS primary care clinics, 50 of 51 primary care providers participated.[24] In the ongoing CHORD study, led by [name], no primary care providers opted out of participation. We conservatively anticipate that 20 of 24 psychiatrists at the VA NYHHS will participate.

CONFIDENTIAL

Psychiatrists who do not opt-out of participation will be randomized to one of the two study arms, stratified by their patient panel size and by the number of patients who smoke (captured as a health factor in the EHR) in their prior-year panel. Randomization will be supervised by the study's statistician. Psychiatrists who opt-out of study participation will receive the opt-in clinical reminder as a part of their routine care, but their performance will not be included in study analyses.

Figure 1. Overview of study design

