4.2 Study Endpoints

4.2.1 Primary Study Endpoints

The study's primary outcomes will measure provider rates of screening and treating their patients for tobacco use in the first 6 months of implementation: 1) the percent of patients screened for tobacco, 2) the percent of smokers prescribed a cessation medication, and 3) the percent of smokers referred to cessation counseling.

5 Study Enrollment and Withdrawal

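### The power statement in 9.3 gives no smoker count for an outcome defined among smokers, and its figures make no small-sample allowance for 10 psychiatrists per arm

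*Combined protocol and SAP*

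**What the plan says.** Section 9.3 contains the plan's only power statement. It concerns the "proportion of patients prescribed a cessation medication by their psychiatrist (primary outcome 2" and assumes 20 psychiatrists, about 4,000 patient visits over six months, 10% prescribed in Arm 1, a type I error of 5% and 80% power. At ICC 0.05, "4,000 visits will provide us with enough power to detect a 21% or greater prescription rate in Arm 2". At ICC 0.15, "4,000 visits will provide us with enough power to detect a 29% or greater prescription rate in Arm 2".

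Section 4.2.1 defines the same outcome as "the percent of smokers prescribed a cessation medication". Section 4.1, the Aim 1 measures in 5.4, Table 2 and section 9.2.2 also restrict it to smokers. Section 9.3 gives neither a smoker count nor a smoking prevalence.

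On the number of psychiatrists, 9.3 says the investigators "have conservatively estimated that 20 will enroll", and 4.1 adds: "We conservatively anticipate that 20 of 24 psychiatrists at the VA NYHHS will participate". Randomisation is "stratified by their patient panel size and by the number of patients who smoke", so smoker counts per psychiatrist are needed before the trial starts. Section 9.2.2 compares the arms with generalised linear mixed models. It names no reference distribution or degrees of freedom for the arm effect, and it does not mention the pre-implementation rates as a covariate, although 4.1, 5.4 and Table 2 collect them.

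**The concern.** Two things that determine power are missing from 9.3. The first is the denominator: it counts visits by patients, while the outcome is measured only in the smokers among them. The second is the number of randomised units. With 10 psychiatrists per arm, the between-psychiatrist variance is estimated on few degrees of freedom, and a normal reference overstates power.

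The analysis is affected as well as the planning. If the arm effect is tested with a default Wald z, the 5% error rate that 9.3 assumes is not guaranteed with so few clusters.

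**Working it through.** **Inputs from the documents.** 20 psychiatrists, 10 per arm (4.1, 9.3); about 4,000 visits, hence m = 200 per psychiatrist; Arm 1 rate 10%; ICC 0.05 and 0.15; 5% type I error; 80% power (9.3).

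**Assumed here.** Equal cluster sizes, a two-sided test, no covariates, and a smoker share of 20-50%, so m = 40 to 100 smokers per psychiatrist.

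**Formulas.** With k psychiatrists per arm:
- design effect DE = 1 + (m − 1) × ICC
- effective number per arm n = k × m / DE
- λ = (p2 − p1) / √{[p1(1 − p1) + p2(1 − p2)] / n}
- normal power = Φ(λ − 1.96)
- small-sample power = P(T > critical value), where T is noncentral t with 2k − 2 df and noncentrality λ

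**Step 1: the plan's figures, all visits.**
- ICC 0.15: DE = 1 + 199 × 0.15 = 30.85; n = 2000 / 30.85 = 64.8; λ = 0.19 / √(0.2959 / 64.8) = 2.81; power Φ(0.85) = 80.3%. The detectable rate at 80% is 28.9%.
- ICC 0.05: DE = 10.95; n = 182.6; λ = 0.11 / √(0.2559 / 182.6) = 2.94; power Φ(0.98) = 83.6%. The detectable rate is 20.4%.

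So 21% and 29% reproduce on a two-sided normal reference, with 20.4% rounded up. They fit as well at an assumed smoker share of 35-50% (21.3/29.5% to 20.9/29.2%). A one-sided 5% test gives 26.5-27.5% at ICC 0.15 and does not fit.

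**Step 2: t reference with 18 df, all visits.** Power is 79.4% at 21% and 75.8% at 29%; detectable rates are 21.1% and 30.2%. The 21% figure alone is therefore compatible with a t, but the 29% figure is not.

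**Step 3: smokers only.** Each pair is for ICC 0.05 / ICC 0.15. Power is at 21% / 29%. The 24-psychiatrist columns use 22 df and the same m.

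| Assumed share (m) | Power, 20 psychiatrists | Detectable rate, 20 | Power, 24 psychiatrists | Detectable rate, 24 |
|---|---|---|---|---|
| 20% (40) | 66.8 / 71.4% | 23.2 / 31.4% | 75.5 / 79.8% | 21.7 / 29.1% |
| 30% (60) | 71.7 / 73.2% | 22.3 / 30.9% | 80.1 / 81.4% | 21.0 / 28.6% |
| 40% (80) | 74.4 / 74.1% | 21.9 / 30.7% | 82.5 / 82.3% | 20.6 / 28.4% |
| 50% (100) | 76.0 / 74.7% | 21.6 / 30.5% | 83.9 / 82.7% | 20.4 / 28.2% |
| All visits (200) | 79.4 / 75.8% | 21.1 / 30.2% | 86.8 / 83.7% | 19.9 / 27.9% |

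At ICC 0.15 with 20 psychiatrists, more patients do not help much. As m grows without limit, n tends to 10 / 0.15 = 66.7 and power at 29% to 76.9%.

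**Step 4: simulation.** Beta-binomial data, cluster-level t test (not the mixed model), 200,000 runs per setting, 10 psychiatrists per arm. With a z critical value the type I error is about 6%. With the 18-df t it is about 4.7-4.8% at ICC 0.05 and about 4.4% at ICC 0.15, so the t is slightly conservative. With the critical value set to give exactly 5% size, power at 21% / 29% is about 80.6 / 78% on all visits and 73 / 76% with 60 smokers per psychiatrist.

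**Step 5: baseline adjustment.** If cluster-level adjustment multiplies the variance by 1 − r², on 17 df, then 80% power at both rates with 20 psychiatrists needs a psychiatrist-level pre-post correlation r of about 0.52, 0.43, 0.37 or 0.36 at shares of 20, 30, 40 or 50%. The documents give no value for r.

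**The case against.** The strongest reply is that 9.3 contains no miscalculation: its rates come out of a standard design-effect formula. That is correct. A reader might infer an arithmetic error, but the documents do not support it. The gap lies in the unstated denominator and the choice of reference distribution.

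A reader might also infer that the sponsor forgot to restrict to smokers. This cannot be shown, because the stated rates fit a smokers-only normal calculation at a 35-50% share about as well as they fit all visits.

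Nor is 76% simply the trial's power at 29%. It comes from an unadjusted cluster-level t test that 9.2.2 does not name and that runs a little below nominal size. With exact size the all-visits figure is about 78%, and the effect is small beside the 21-29% spread that 9.3 already shows for an unknown ICC.

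Finally, 9.3 calls 20 psychiatrists conservative, and 24 would largely close the gap. Baseline rates are collected too, and 9.2.2 does not exclude adjusting for them. These offsets are real, but 9.3 claims its 80% for 20 psychiatrists and counts neither offset. At a 20% share, even 24 psychiatrists give 75.5% at 21%. With 60 smokers per psychiatrist and 20 psychiatrists, power stays below 80% even at exact size.

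**Conclusion.** The point holds as a gap in specification that should be corrected. It does not invalidate the design. The missing smoker count follows from the text alone. The missing small-sample allowance is inferred from the pair of rates, and chiefly from the 29% figure.

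The size depends on the denominator. On all visits the shortfall is nil at ICC 0.05 and about 2 to 4 points at ICC 0.15. On smokers only, with 20 psychiatrists and an 18-df t, power is about 67-76% at 21% and 71-75% at 29%, and detectable rates are about 1 to 2 points above those stated. With 24 psychiatrists, power reaches 80% at both rates from about a 30% share.

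These results rest on equal clusters, no covariates and an assumed smoker share. Unequal panels would lower power; useful baseline adjustment would raise it.

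**What to change.** **In 9.3:** state that the outcome is analysed among smokers, and base the calculation on expected smokers per psychiatrist, taken from the prior-year counts already needed for stratification. Use a small-sample reference, for example t with df equal to the number of psychiatrists minus 2, less one for each psychiatrist-level covariate fitted. Restate the power or the detectable rates for both 20 and 24 psychiatrists. With 20, unadjusted, and 40-100 smokers each, the detectable rates are about 21.6-23.2% at ICC 0.05 and 30.5-31.4% at ICC 0.15.

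**In 9.2.2:** test the arm effect in the mixed model against a small-sample reference such as that t, in place of a default Wald z. Adjust for each psychiatrist's pre-implementation rate. Other small-sample methods would also serve, provided that one is fixed before analysis.

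**Cost:** a text change with no extra patients or data collection. The stated detectable rates become about 1 to 2 points less favourable with 20 psychiatrists, and the test slightly more conservative.

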10.1 Ethical Standard

The investigator will ensure that this study is conducted in full conformity with Regulations for the Protection of Human Subjects of Research codified in 45 CFR Part 46.

10.2 Institutional Review Board

The protocol, waiver applications, recruitment materials, and all participant materials will be submitted to the IRB for review and approval. Approval of both the protocol and the consent form must be obtained before any participant is enrolled. Any amendment to the protocol will require review and approval by the IRB before the changes are implemented to the study. All changes to the consent form will be IRB approved; a determination will be made regarding whether previously consented participants need to be re-consented.

10.3 Informed Consent Process

10.3.1 Consent/Assent and Other Informational Documents Provided to Participants

Consent forms describing in detail the study intervention, study procedures, and risks are given to the participant and written documentation of informed consent is required prior to starting intervention. The following consent materials are submitted with this protocol:

- Informed Consent (for psychiatrists) for qualitative interview
- Audio Recording Consent (for psychiatrists)
- Waiver of Documentation of Consent (Psychiatrist Study Population)
- Waiver of Documentation of Consent (Patient Post-Visit Survey Population)

CONFIDENTIAL

A waiver of authorization and a waiver of consent and documentation of consent have been submitted for IRB approval.

10.3.2 Consent Procedures and Documentation

Psychiatrists will have the option to decline study participation at any point in the study. Psychiatrists who opt-out of study participation will receive the opt-in clinical reminder as part of their routine care, but their performance will not be included in study analyses. We will include a cover letter on the survey including all elements of informed consent. Completing the survey will serve as documentation of consent from psychiatrists for the baseline/6-month surveys. Psychiatrists face minimal risk by participating in this study and are able to withdraw at any time. During the consent process, subjects are able to express any questions or concerns with the research team. Research staff will request separate participant consent for participation in the qualitative interviews and for audio recording.

Patient Post-Visit Survey Population (n=400). We will obtain a waiver of HIPAA authorization to identify smokers through CPRS. We will obtain verbal consent from participants for completing the short post-visit survey, and thus will obtain a waiver of documentation of consent. The consent will cover the post-visit survey and consent to participate in a short survey 6 months later to assess their use of cessation treatment and abstinence outcomes. As the survey will be conducted over the phone, it will not be possible to have documented informed consent.

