5.6.2 Handling of Participant Withdrawals or Termination

After a participant withdraws, the study will not conduct any additional follow-up with the participant. Participants who withdraw will not be replaced.

6 Behavioral/Social Intervention

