To reinforce provider self-efficacy in treating mental health patients for smoking, we will also implement academic detailing (educational outreach) for providers in both arms. Academic detailing has consistently shown improvements in provider behavior.[30] Two study investigators will make a brief outreach visit to each psychiatrist, at least one of whom will be a physician to answer any questions about cessation medications. The investigators will follow a script, using the seven steps recommended by the National Resource Center for Academic Detailing:[31] 1) The Introduction; 2) Needs Assessment; 3) Key Messages/Features/Benefits; 4) Understanding Barriers and Enablers; 5) Identifying and Handling Objections; 6) Summary; and 7) Close. The key message (Step 3) will include demonstration of the clinical reminder, review of the evidence for smoking cessation medications and how to prescribe them, and review of the role of the facility Health Promotion staff and how to contact them. Note that detailing will occur after randomization, so each psychiatrist will receive a detailing visit on the specific intervention to which he or she will be exposed.

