7.1.1 Study Specific Procedures

7.1.1.1 Psychiatrist training

One month before implementation of the provider training and reminders, all psychiatrists in the facility will be notified of the study at a required staff meeting.. [name] will deliver a psychiatrist training adapted from [name], tailored for training psychiatrists on tobacco use cessation for mental health patients.

7.1.1.2 Provider Randomization and Baseline Survey.

Psychiatrists will be approached and given the opportunity to choose to participate in the study or opt out of participating. At this time, psychiatrists will also have the option to ask questions. Completion of the baseline survey during this point will serve as study assent and psychiatrist will then be randomized into the control group or the intervention group.

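### Section 10.3.2, read literally, drops psychiatrists who leave after randomisation from the analyses, and section 9.2.2 names no primary Aim 1 set that would keep them (minor, cheap to fix)

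*Combined protocol and SAP*

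**What the plan says.** Section 10.3.2 opens: "Psychiatrists will have the option to decline study participation at any point in the study". Its next sentence says that psychiatrists who opt out "will receive the opt-in clinical reminder as part of their routine care, but their performance will not be included in study analyses". No time limit is attached. Later in the same paragraph: "Psychiatrists face minimal risk by participating in this study and are able to withdraw at any time".

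Section 4.1 has almost the same exclusion sentence in a different setting. Opt-out is offered at a staff meeting one month before implementation, and then: "Psychiatrists who do not opt-out of participation will be randomized to one of the two study arms". Section 7.1.1.2 gives the same order: "Completion of the baseline survey during this point will serve as study assent and psychiatrist will then be randomized".

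Section 6.1 shows when arms become known: "Note that detailing will occur after randomization, so each psychiatrist will receive a detailing visit on the specific intervention".

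On later exit, section 5.6.2 says: "After a participant withdraws, the study will not conduct any additional follow-up with the participant". It adds that leavers are not replaced and says nothing about the analysis set.

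Section 9.2.2 deals with missing data and dropout in Aim 1 through sensitivity analyses, within which intention-to-treat is set against complete case. It does not say which is primary for Aim 1. For Aim 3 it does: complete case.

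**The concern.** The psychiatrist is the unit of randomisation, with 10 planned per arm. If the exclusion in 10.3.2 covers those who leave after randomisation, whole clusters drop out of the comparison when their arm is already known to them.

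Leaving could depend on the arm. Under 10.3.2 an Opt-Out psychiatrist who leaves moves to the opt-in reminder, while a control psychiatrist who leaves sees little change. Section 6.1.2 itself expects some reluctance: one listed reason for cancelling an order is that the psychiatrist does not wish to treat at that visit. If reluctant prescribers were the ones to leave Opt-Out, the remaining Opt-Out psychiatrists would look better than the randomised group.

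The intention-to-treat comparison in 9.2.2 would not reveal this. If leavers are out of all study analyses, the intention-to-treat set cannot contain every randomised psychiatrist either.

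**Working it through.** **1. The passages side by side**

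| Question | 4.1 and 7.1.1.2 | 10.3.2 | 5.6.2 | 9.2.2 (Aim 1) |
|---|---|---|---|---|
| When can a psychiatrist leave? | Before randomisation | At any time | At any time (with 5.6.1) | Not stated |
| Are the leaver's data analysed? | No (never randomised) | No, without time limit | Not stated | Dropout named for sensitivity analysis; primary set not named |

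No section says that a randomised psychiatrist who leaves stays in the Aim 1 analysis.

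**2. The plan's own power figures**

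Inputs from section 9.3: 20 psychiatrists, about 4,000 visits, 10% in Arm 1, ICC 0.05 and 0.15, type I error 5% (taken as two-sided), power 80%. Visits per psychiatrist: m = 4,000/20 = 200. Design effect = 1 + (m − 1) × ICC.

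- ICC 0.05: 1 + 199 × 0.05 = 10.95; effective n per arm = 2,000/10.95 = 182.6; detectable rate 20.6% (plan: 21%).
- ICC 0.15: 1 + 199 × 0.15 = 30.85; effective n per arm = 2,000/30.85 = 64.8; detectable rate 29.4% (plan: 29%).

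The figures reproduce. The detectable differences are 21 − 10 = 11 and 29 − 10 = 19 points.

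**3. What dropping Opt-Out leavers would do**

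The following are assumptions, not in the documents: one or two leavers, all from Opt-Out; 40, 60, 100 or 200 smokers per psychiatrist; psychiatrist rates following a Beta distribution with mean 10% in both arms (no true effect) and the plan's ICCs; and a two-sample t test on cluster proportions in place of the planned mixed model. Each setting has 40,000 simulated trials. Ranges span both ICCs and all four cluster sizes.

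| Who leaves Opt-Out | Bias (points) | Two-sided error | False positives favouring Opt-Out |
|---|---|---|---|
| Nobody | 0 | 4.3–4.8% | 2.0–2.4% |
| One, at random from the lower half | +0.5 to +0.9 | 4.5–5.0% | 3.2–3.6% |
| Two, at random from the lower half | +1.1 to +1.9 | 5.8–6.3% | 4.9–5.5% |
| Exactly the lowest | +0.8 to +1.1 | 5.3–6.4% | 4.3–4.9% at 60 smokers |
| Exactly the two lowest | +1.7 to +2.4 | 7.9–9.9% | 7.4–8.0% at 60 smokers |
| Any, at random | within 0.1 | 4.2–4.8% | not tabulated |

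Under random exit the cost is power. At 60 smokers each, with nobody, one or two leaving:

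- 10% against 21%, ICC 0.05: 72.4%, 70.6%, 68.1%.
- 10% against 29%, ICC 0.15: 73.8%, 72.0%, 69.8%.

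Over all cluster sizes the loss is 1.7 to 2.3 points with one exit and 3.8 to 5.0 points with two.

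**The case against.** The strongest reply is that the literal reading is not the natural one. Wherever the protocol gives the timing of the opt-out (4.1, 7.1.1.2, 7.1.1.3), it comes before randomisation. The sentence in 10.3.2 nearly duplicates the one in 4.1, and the same paragraph of 10.3.2 uses a different verb, withdraw, for later exit. This stands, and it is why the point is minor. It does not close the point, because the sentence just before the exclusion removes any time limit and no section says what happens to a withdrawer's data.

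Little attrition is also expected. Section 4.1 reports low turnover, enrols only psychiatrists with no plan to leave within 6 months, notes that in an earlier study "50 of 51 primary care providers participated", and says that no provider opted out of an ongoing one. This supports a small likely effect. The provider figures, however, concern agreeing to take part, not leaving after allocation.

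Dropout sensitivity analyses are already planned. That stands in part: the contrast is foreseen, but neither side of it is named as primary for Aim 1.

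Three stronger inferences are tempting and are not supported:

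- *That 10.3.2 breaches a declared intention-to-treat primary analysis.* Section 9.2.2 declares none for Aim 1.
- *That 5.6.2 confirms the exclusion.* It covers further follow-up and replacement. The primary outcomes come from EHR extracts, and it does not say that data are removed.
- *That the error is seriously inflated.* A type I error near 20% appears only if the four lowest of ten Opt-Out prescribers leave and nobody else does. Nothing in the documents suggests this.

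**Conclusion.** The point holds as an ambiguity with a small likely effect. Followed as written, 10.3.2 excludes randomised clusters after their arm is known, and 9.2.2 contains no rule that overrides it. Whether the authors meant this cannot be settled from the documents.

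The size depends on exits that have to be assumed. One lower-half Opt-Out leaver does not raise two-sided error above 5%. Two raise it to about 6%, with a shift of under 2 points against detectable differences of 11 and 19. The 8 to 10% figure is a worst case that needs exactly the two lowest Opt-Out prescribers to leave. Exit unrelated to prescribing costs only power. All of this concerns the prescription outcome; screening and referral were not simulated and no effect on them is claimed. Severity: minor.

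**What to change.** - **10.3.2:** limit the exclusion from analyses to psychiatrists who opt out before randomisation, as the sequence in 4.1 implies.
- **9.2.2:** state that the primary Aim 1 analysis includes all randomised psychiatrists and their patients in the assigned arm, using the 6-month EHR extract as far as the consent and authorization waivers allow. Keep exclusion of leavers as the sensitivity analysis already foreseen for dropout, and report withdrawals by arm.
- **4.1 and 5.6.2:** align the wording with these two changes. Which reminder a leaver then receives is for the investigators to decide.

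The cost is one sentence in each of 10.3.2 and 9.2.2, plus the alignment, with no new data collection. The one real task is to confirm that the waivers described in 10.3.1 and 10.4 cover EHR data after a psychiatrist leaves. Those applications are not in the documents, and if they do not cover such data, the plan should say so and give the analysis set that results.
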